11.3.4.3 Average Monthly IV iron use in 2nd and 3rd year of treatment

The same analysis of 11.2.1.4 will be perform for the above endpoint.

11.3.5 Changes in Cholesterol Levels

- Change at each of the selected treatment time points in:
 - total cholesterol,

- low-density lipoprotein/high-density lipoprotein ratio,
- non-HDL cholesterol.

The mean change in these 3 endpoints at each post-dosing time point will be analyzed and compared between the 2 treatment groups using the MMRM model with baseline value as a covariate, treatment, visit and interaction of treatment and visit and stratification factors as fixed effects. The same strategy as that used in MMRM in Section 11.1.3.1 will be used to choose variance covariance. Data up to visit of Week 52 will be included in the analyses.

- Proportion of subjects achieving LDL target of <100 mg/dL averaged over Weeks 12-24 of treatment. The proportion of subjects achieving LDL target will be compared between the 2 treatment groups using logistic regression model adjusting for baseline LDL value and baseline stratification factors as fixed effects.

11.3.6 Blood Pressure Effect

- Proportion of subjects achieving blood pressure treatment goal in ESRD subjects (pre dialysis systolic BP <140 mmHg systolic and diastolic BP<90 mmHg) averaged over Weeks 12-28. The proportion of subjects achieving blood pressure goal will be compared between the 2 treatment groups using logistic regression model adjusting for baseline pre dialysis systolic and pre dialysis diastolic blood pressures as covariates and baseline stratification factors as fixed effects.
- Mean change in mean arterial pressure (MAP) averaged over Weeks 20-28

The same analysis as 11.2.1.5 will be performed for the above endpoint.

11.3.7 Vascular Access Thrombosis

- Time to a treatment-emergent AE of vascular access thrombosis
- Proportion subjects with a treatment-emergent AE of vascular access thrombosis

11.3.8 Health Related Quality of Life (HRQoL) and EQ-5D-5L Benefits of Anemia Therapy

The Medical Outcomes Study 36-Item Short-Form Health Survey (SF-36) is a multi-purpose, short-form health survey with 36 questions (see appendix 2). It yields an 8-scale profile of functional health and well-being scores as well as psychometrically-based physical and mental health summary measures. It is a generic measure, as opposed to one that targets a specific age, disease, or treatment group. Accordingly, the SF-36 has proven useful in surveys of general and specific populations, comparing the relative burden of diseases, and in differentiating the health benefits produced by a wide range of different treatments.

[figure not shown]
The SF-36 contains 36 items that measure eight dimensions: (1) physical functioning (PF); (2) role limitations due to physical health problems (RP); (3) bodily pain (BP); (4) social functioning (SF); (5) general health perceptions (GH); (6) role limitations due to emotional problems (RE); (7) vitality, energy or fatigue (VT); and (8) mental health (MH).

Table 6 Transformation of SF-36 items to a scale from 0 to 100

Question	Self-perceived health	
	0 (Poor)	100 (Better)
1, 2, 6, 8, 9a, 9d, 9e, 9h, 11b, 11d	5	1
3a to 3j	1	3
4a to 4d, 5a to 5c, 9b, 9c, 9f, 9g, 9i, 10, 11a, 11c	1	5
7	6	1
Programming note: Once transformed – the items should each span the range 0 to 100.		

Item scores for each dimension are coded, summed, and transformed to a scale from 0 to 100, with higher scores indicating better self-perceived health (See detail in 4). The transformed items are then averaged to give the subscales. The subscales are averaged to give the composite scores. The composite scores are averaged to give the overall score. The reliability and validity of the SF-36 is well documented in a variety of different patient groups, including patients with vascular diseases.

For each of the 8 dimensions, if less than 50% of the items which constitute that dimension are missing, the dimension score will be calculated by the mean of the available non-missing items. The physical health composite summary and mental health composite summary will only be calculated if a score has been calculated for all 4 dimensions that constitute the composite summary.

Figure 1. SF-36 Model

The mean change from baseline at weeks 12, 36, and 52 weeks will be computed for each treatment group. A paired t-test will be used to assess within treatment effect. Between treatment difference will be assessed using the MMRM model with baseline sub-score as a covariate, and treatment group, visit, interaction of treatment and visit, and stratification factors as fixed effects. The same strategy as that used in MMRM in Section 11.1.3.1 will be used to choose variance covariance. Data up to visit of Week 52 will be included in the analyses. Non-inferiority of roxadustat vs. ESA will be tested. The non-inferiority margin is fixed as a difference of 2 points.

HRQoL benefit will also be assessed using SF-36 vitality and physical functioning subscales. Mean change in following endpoints at above-mentioned time points will be analyzed and compared between the 2 treatment groups using MMRM using the baseline value as a covariate, treatment group, visit, the interaction of treatment and visit, adjusting for the stratification factors. The same strategy as that used in MMRM for Hb will be used to choose variance covariance structure. Other than below endpoints for exploratory analyses, other QoL variables may be performed

- Vitality Subscale of SF-36: In FAS subjects with baseline Vitality Sub-score below 50.
- Physical Component Scores of SF-36:
 - In FAS subjects with baseline *physical component scores* below 40.
 - In all FAS subjects.
- Anemia Subscale (“Additional Concerns”) of Functional Assessment of Cancer Therapy-Anemia (FACT-An) Scores:
 - In FAS subjects with baseline subscale scores below 55 (generally associated with fatigue).
 - In all FAS subjects.
- Total FACT-An Scores:
 - In FAS subjects with baseline FACT-An scores below 135
 - In all FAS subjects.
- EQ-5D-5L Scores: In all FAS subjects.

11.3.9 Hepcidin, Iron, and HbA1c

The mean change from baseline in the following endpoints will be analyzed using the MMRM model with baseline value as a covariate and treatment group and stratification factors as fixed effects with the same strategy as that used in MMRM in Section 11.1.3.1 will be used to choose variance covariance and data up to visit of Week 52 will be included in the analyses:

- Change from baseline in serum hepcidin at each of the selected time points (e.g., Weeks 4, 12, 20, 44 and every 8 weeks onwards)

- Change from baseline in CHr at each of the selected time points (e.g., Weeks 4, 8, 12, 20, 28, and every 8 weeks onwards)
- Change from baseline in serum ferritin at each of the selected time points, total and sub-grouped by baseline values of <100 ng/mL, 100 to <400 ng/mL and >=400 ng/mL.
- Change from baseline in TSAT at each of the selected time points, total and sub-grouped by baseline values of <20%, 20% to <40%, and >=40%.
- Serum iron at each of the time points tested
- CHr at each timepoint tested (Weeks 4, 8, 12, 20, 28, 36, every 8 weeks onwards)
- Proportion of patients with CHr > ULN at each timepoint tested: Weeks 4, 8, 12, 20, 28, 36, every 8 weeks onwards)
- Change in HbA1c level at each of the selected time points in subjects without history of diabetes, in subjects with history of diabetes.

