4.4 ADDITIONAL EVALUATION OF EFFICACY

The additional efficacy evaluations in this study are:

- **Hb Correction and Maintenance:**
 - Hemoglobin maintenance: Mean change from baseline in Hb averaged over 8 weeks of treatment at Weeks 28 to 36, without rescue therapy within 6 weeks prior to and during this 8-week evaluation period.
 - Hemoglobin long-term Maintenance: Mean change in Hb averaged over 8 weeks of treatment at Weeks 44-52 without rescue therapy within 6 weeks prior to and during this 8-week evaluation period.
 - Mean change from baseline in Hb averaged over the 96 to 104 weeks of treatment, without rescue therapy within 6 weeks prior to and during this 8-week evaluation period.
 - Change from baseline in Hb at each of the selected post-dosing time points.
 - Proportion of subjects with Hb ≥ 10 g/dL averaged over Weeks 28-36, without rescue therapy within 6 weeks prior to and during this 8-week evaluation period.
 - Proportion of subjects with mean Hb < 9 g/dL, 9- <10 , 10- <11 , 11- <12 , 12- <13 , ≥ 13 g/dL during Weeks 28-36
 - Proportion of patient exposure (PEY) with Hb < 9 g/dL, 9- <10 , 10- <11 , 11- <12 , 12- <13 , ≥ 13 g/dL during weeks 28 to 52
- **Hospitalizations:**
 - Time to first hospitalization (% of subjects) up to Week 52.
 - Time to first hospitalization or skilled nursing facility (% of subjects) up to Week 52
 - Number of days of hospitalizations per patient-exposure year (PEY).
 - Number of days of hospital or skilled nursing facility per PEY
 - Number of medical-facility free days (hospital, skilled nursing facility, emergency room, or overnight observation) per PEY
 - Number of days on treatment out of hospital and skilled nursing facility up to Week 52, 7 days after Last Dose.
- **Missed dialysis sessions up to Week 52**
 - Occurrence (number) of missed dialysis sessions
 - Proportion of subjects with missed dialysis sessions
 - Number of days of missed dialysis sessions per patient-exposure year (PEY)

- **Rescue Therapy Use up to Week 52:**
 - Proportion of subjects who receive RBC transfusions.
 - Number of RBC packs per patient-month exposure to study medication.
 - Roxadustat subjects: The proportion of subjects requiring ESA rescue therapy (ATC code: B03XA01)
- **Changes in Cholesterol Levels:**
 - Change at each of the protocol specified treatment time points in:
 - total cholesterol,
 - low-density lipoprotein (LDL)/high-density lipoprotein (HDL) ratio,
 - non-HDL cholesterol.

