 - Proportion of subjects achieving LDL target of <100 mg/dL averaged over Weeks 12-24 of treatment.
- **Blood Pressure Effect:**
 - Time to an exacerbation of hypertension over weeks 28-52, meeting at least 1 of the following criteria: Increase in blood pressure: An increase from baseline of ≥ 20 mm Hg systolic BP and sBP >170 mmHg or an increase from baseline of ≥ 15 mm Hg diastolic BP and dBP >100 mmHg.
 - Proportion of subjects achieving blood pressure treatment goal in ESRD subjects (pre dialysis systolic BP <140 mmHg and diastolic BP <90 mmHg) averaged over Weeks 12-28.
- **Health Related Quality of Life (HRQoL) and EQ-5D-5L Benefits of Anemia Therapy:**

Mean change averaged over Weeks 12, 36 and 52 of treatment including those listed below.

 - Vitality Sub-score of SF-36:
 - In FAS subjects with baseline Vitality Sub-score below 50.
 - In all FAS subjects.
 - Physical Functioning Sub-scores of SF-36:
 - In FAS subjects with baseline *Physical Functioning Sub-scores* below 40.
 - In all FAS subjects.
 - Anemia Subscale (“Additional Concerns”) of Functional Assessment of Cancer Therapy-Anemia (FACT-An) Scores:
 - In FAS subjects with baseline subscale scores below 55 (generally associated with fatigue).
 - In all FAS subjects.

- Total FACT-An Scores:
 - In FAS subjects with baseline FACT-An scores below 135
 - In all FAS subjects.
- EQ-5D-5L Scores and other QoL Measures/Other Component scores of SF-36: In all FAS subjects.
- **Hepcidin, Iron, C_Hr and HbA1c:**
 - Change from baseline in serum hepcidin at each of the selected time points (e.g., Weeks 4, 12, 20, 44 and every 8 weeks onwards)
 - Change in serum iron from baseline to Week 28
 - Change in TSAT from baseline to Week 28
 - Change from baseline in serum ferritin at each of the selected time points, total and sub-grouped by baseline values of, ≥ 400 ng/mL, 400 to 100 ng/mL, and <100 ng/mL.
 - Change from baseline in TSAT at each of the selected time points, total and sub-grouped by baseline values of $\geq 40\%$, 40% to 20%, and $<20\%$.
 - Serum iron at each of the time points tested
 - Change from baseline in C_Hr at each of the selected time points (e.g., Weeks 4, 8, 12, 20, 28, 36 and every 8 weeks onwards)
 - Proportion of patients with C_Hr $>$ LLN at each timepoint tested: Weeks 4, 8, 12, 20, 28, 36, and every 8 weeks onwards)

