5.3 METHODOLOGY AND CONVENTIONS

Safety and efficacy data will be summarized and presented by treatment group and time point in summary tables. Continuous variables will be presented by descriptive statistics: n, mean, standard deviation, median, minimum, and maximum. Categorical variables will be tabulated by frequency count and percentage.

Lab results obtained from the central laboratory, rather than local laboratories, will be used for all efficacy and safety analyses. Local laboratory values, if collected in the CRF's, will be listed only in data listing.

When the actual treatment received by a subject is different from the randomized treatment assigned, the subject will be analyzed per the randomized treatment for the efficacy parameters; while they will be analyzed per actual treatment that was taken for the safety parameters for US submission.

Unless otherwise stated, all statistical tests will be two-sided hypothesis tests performed at the 5% level of significance for main effects and all confidence intervals will be two-sided 95% confidence intervals.

The secondary endpoints will be tested sequentially using the fixed sequence approach for multiplicity adjustments at an alfa level of 0.05. There will be no adjustments for multiple comparisons for other tests.

All analyses will be performed using SAS® Version 9.1.3 or higher.

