APPENDIX 3: RANGES OF POTENTIALLY CLINICALLY SIGNIFICANT LAB VALUES

Parameter	SI Unit	Lower Limit	Higher Limit
CHEMISTRY			
Alanine Aminotransferase (ALT)	U/L		≥3 * ULN
Alkaline Phosphatase	U/L		≥3 * ULN
Aspartate Aminotransferase (AST)	U/L		≥3 * ULN
GGT	U/L		≥3 * ULN
Calcium	mmol/L	<0.8*LLN	>1.2 * ULN
Creatinine	µmol/L		> 1.5x Baseline value
Potassium	µmol/L	<0.75*LLN	>1.2 * UNL
Sodium	mmol/L	<0.9*LNL	>1.1 * UNL
Total Bilirubin	µmol/L		>1.5 * UNL
Total Protein	µmol/L	<0.9*LNL	>1.1 * UNL
Urea (BUN)	mmol/L		>1.5X Baseline value
HEMATOLOGY			
Neutrophils	10 ⁹ /L	≤1	
Platelet Count	10 ⁹ /L	≤ 100	≥700
White Blood Cell Count	10 ⁹ /L	≤2.5	≥15
LLN: Lower limit of normal, value provided by the laboratory			
ULN: Upper limit of normal, value provided by the laboratory			

16.4

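### SAP section 4.4 lists the CHr proportion endpoint as above the lower limit of normal, but section 11.3.9 analyses it as above the upper limit

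*SAP*

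**What the plan says.** SAP section 4.4, in its group on hepcidin, iron, CHr and HbA1c, lists this endpoint: "Proportion of patients with C_Hr $>$ LLN at each timepoint tested". The weeks are 4, 8, 12, 20, 28, 36 and every 8 weeks after that.

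SAP section 11.3.9 lists the analyses for the same group. Its entry is "Proportion of patients with CHr > ULN at each timepoint tested", with the same weeks.

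SAP Appendix 3 gives the two abbreviations distinct meanings: "LLN: Lower limit of normal, value provided by the laboratory" and "ULN: Upper limit of normal, value provided by the laboratory".

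On status, section 4.4 opens with "The additional efficacy evaluations in this study are", and section 5.3 says of tests outside the secondary sequence: "There will be no adjustments for multiple comparisons for other tests".

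**The concern.** The endpoint list and the analysis section describe what appears to be one endpoint, with two different cut-offs. Each section gives only one of them. If tables are built from section 11.3.9 as it stands, they will show the share of patients with supranormal CHr. The endpoint that section 4.4 promises, the share above the lower limit, will not be reported.

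The study is open-label, and protocol section 8.4.5 ties early finalisation of the SAP to avoiding bias. A threshold left unresolved would have to be settled later, possibly once CHr data by arm are visible. The stake is small because the endpoint is a minor one, but the ambiguity is avoidable.

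**Working it through.** **Step 1: compare the two entries.**

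| Item | SAP 4.4 | SAP 11.3.9 |
|---|---|---|
| Measure | proportion of patients | proportion of patients |
| Analyte | CHr | CHr |
| Weeks | 4, 8, 12, 20, 28, 36, then every 8 | 4, 8, 12, 20, 28, 36, then every 8 |
| Direction | above | above |
| Threshold | lower limit of normal | upper limit of normal |

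Only the threshold differs. The decisive words in section 4.4 are "LLN at each timepoint tested: Weeks 4, 8, 12, 20, 28, 36".

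**Step 2: look for text that settles it.**

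- Protocol section 7.3 covers hepcidin, ferritin, TSAT and HbA1c in the matching group. It has no CHr proportion endpoint, so the protocol cannot decide between the two.
- SAP section 11.3 points to section 4.3 for the additional endpoints, but they are in section 4.4. The cross-reference therefore does not lead the reader to the lower-limit definition.
- Neither document says which SAP section takes precedence, or that two CHr proportion endpoints are intended.
- Protocol section 1.4.2.2, on the conversion study in US dialysis subjects, reports that CHr was better maintained on roxadustat than on epoetin alfa and takes this as a sign that functional iron deficiency did not occur. That argument concerns CHr not falling too low, which fits a lower-limit cut-off. It sets no threshold.

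**Step 3: size of the discrepancy.** The plan states no expected rate for this endpoint, so there is no figure to reproduce. One relation holds for any distribution:

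P(CHr > LLN) − P(CHr > ULN) = P(LLN < CHr ≤ ULN)

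The gap between the two reported proportions is thus the share of patients inside the normal range (above the lower limit and not above the upper).

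To put numbers on it I make three assumptions, none of them in the documents: CHr is normally distributed; the laboratory limits are a central 95% reference interval, so they lie at ±1.96 SD; and the study population has the reference SD, with its mean shifted by *s* SD. Then, with Φ the standard normal distribution function:

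- P(CHr > LLN) = 1 − Φ(−1.96 − s)
- P(CHr > ULN) = 1 − Φ(1.96 − s)

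| Mean shift *s* (SD) | Above LLN (%) | Above ULN (%) | Gap (percentage points) |
|---|---|---|---|
| −2 | 48.4 | 0.004 | 48.4 |
| −1 | 83.15 | 0.154 | 83.0 |
| −0.5 | 92.79 | 0.695 | 92.1 |
| 0 | 97.5 | 2.5 | 95.0 |
| +0.5 | 99.31 | 7.215 | 92.1 |
| +1 | 99.85 | 16.854 | 83.0 |

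For example, at s = −2 the lower-limit figure is 1 − Φ(0.04) = 48.4% and the upper-limit figure is 1 − Φ(3.96) = 0.004%. Across this range the two definitions never give similar answers.

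**The case against.** The strongest reply is that the documents do not prove which threshold is right. Section 4.4 gives no rationale for its cut-off, the protocol lists no such endpoint, and the phase 2 remark about CHr names no limit. That stands, and it is why the sponsor should confirm before the text is changed. It does not remove the mismatch, since the two sections cannot both describe one endpoint.

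A reader might infer more than the texts support:

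- *That the two proportions answer opposite questions.* They do not. Both count patients above a cut-off, and everyone above the upper limit is also above the lower. They are nested and measure different things.
- *That the tables will be produced with the upper limit.* SAP section 1 puts table specifications in a separate document of table shells, which is not available here. What the shells say is unknown; the point is limited to section 11.3.9 as written.
- *That the SAP defines an iron-sufficiency responder endpoint.* The SAP speaks only of a proportion of patients. The link to iron supply is an interpretation drawn from the protocol's background section.
- *That the result must move from most patients to few.* This depends on an unstated CHr distribution. In the −2 SD case, fewer than half exceed even the lower limit.

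It is also fair to say that little depends on this endpoint. CHr change from baseline and CHr at each time point are reported as well, and SAP section 12.2 adds descriptive summaries.

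**Conclusion.** The inconsistency is real: as written, SAP section 11.3.9 does not analyse the CHr proportion that section 4.4 lists. The lower limit is the better-supported reading, because it is the one in the endpoint list and it fits the functional iron deficiency rationale in protocol section 1.4.2.2. It remains an inference.

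Under normality, a central 95% reference interval and an unchanged SD, the two definitions differ by 48.4 to 95.0 percentage points over mean shifts from −2 to +1 SD. These figures show scale only and are not predictions for this trial.

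The reach is narrow. This is an additional efficacy evaluation with no multiplicity control. The primary endpoints, the fixed secondary sequence, sample size and power do not depend on it. It is a minor correction that is worth making.

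**What to change.** Ask the sponsor to confirm that the lower limit of normal is intended. Once it is confirmed, replace ULN with LLN in the CHr proportion entry of section 11.3.9, so that sections 4.4 and 11.3.9 use one threshold, and check the table shells against it. If both proportions are in fact wanted, list both in both sections. The cost is one word in the SAP and a short check, best done before the tables are programmed.

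A separate gap could be closed in the same edit. Section 11.3.9 opens its list with "The mean change from baseline in the following endpoints will be analyzed using the MMRM model with baseline value as a covariate", which does not suit a proportion, whereas protocol section 8.4.3.3 names CMH for additional proportion endpoints. Changing the threshold alone leaves the method for this item unstated, so one should be named.

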12 SAFETY ANALYSES

The safety analysis will be performed using the Safety Population. Safety parameters include adverse events, laboratory parameters, vital signs, ECG parameters, and physical examinations.

Safety interpretation will also be made based on analyses of composite endpoints derived from adjudicated events pooled across multiple studies in the roxadustat Phase 3 program per pooled statistical analysis plan (PSAP) on dialysis studies in the roxadustat program.

For each safety parameter, the last assessment made prior to the first dose of study medication will be used as the BL for all analyses of that safety parameter.

12.1 ADVERSE EVENTS

Adverse events will be coded using the latest MedDRA version.

12.1.1 Proportion of Subjects with TEAE

An AE (classified by preferred term) started during the treatment period will be considered a treatment-emergent adverse event (TEAE) if it was not present prior to the first dose of study medication, or it was present prior to the first dose of study medication but increased in severity during the treatment period up to 7 days after last dose of study drug or until the administration of another anemia drug (other than the randomized treatment). An AE that occurs more than 7 days after the last dose of study medication or after the administration of another anemia drug (other than the randomized treatment) will not be counted as a TEAE.

The number and percentage of subjects reporting TEAEs in each treatment group will be tabulated separately by system organ class and preferred term; by system organ class, preferred term, and severity; and by system organ class, preferred term, and relationship to study medication. If more than one event occurs with the same preferred term for the same patient, the patient will be counted only once for that preferred term using the most severe and most related occurrence for the summarization by severity and by relationship to the study medication.

The distribution of TEAEs by severity and relationship to study medication will be summarized by treatment group.

The incidence of common ($\geq 5\%$ of subjects in any treatment group) TEAEs, treatment-emergent serious AEs (TESAE), and AEs leading to discontinuation of study medication will be summarized by preferred term and treatment group, sorted in decreasing overall (across treatments) frequency. In addition, the incidence of death and fatal SAEs (i.e., events that caused death) and incidence rate per PEY will be summarized separately by treatment group and preferred term.

Listings will be presented of subjects with serious adverse events (SAEs), subjects with adverse events leading to discontinuation, and subjects who died.

Temporal profile of TEAEs of special interest may also be plotted by treatment group showing the subjects in the y-axis and time to these TEAEs in the x-axis (Appendix 8).

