##### **8.4.4.1 Adverse Events**

Adverse events will be coded using the Medical Dictionary for Regulatory Activities (MedDRA).

An AE (classified by preferred term) occurring during the Treatment Period will be considered a TEAE if it was not present prior to the first dose of study medication, or if it was present prior to the first dose of study medication but increased in severity during the Treatment Period. An AE that occurs more than 28 days after the EOT/ET visit date will not be counted as a TEAE.

The number and percentage of subjects reporting TEAEs in each treatment group will be tabulated by system organ class and preferred term; by system organ class, preferred term, and severity; and by system organ class, preferred term, and relationship. If more than one event occurs with the same preferred term for the same subject, the subject will be counted only once for that preferred term using the most severe and most related occurrence for the summarization by severity and by relationship to the study medication.

The overall distribution of TEAEs by severity and relationship to study medication will be summarized by treatment group.

The proportion of subjects with TESAEs, fatal SAEs (ie, events that caused death), and AEs leading to discontinuation of study medication will be summarized by SOC, preferred term and treatment group.

Treatment emergent adverse events of interest will also be reported in terms of incidence rate per PEY.

Listings will be presented of subjects with SAEs, subjects with AEs leading to discontinuation, and subjects who died.

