### **8.4.5 Statistical Analysis Plan**

The Statistical Analysis Plan will provide details of the data analyses. As an open-label study the SAP will be finalized prior to accumulation of a substantial amount of data to ensure lack of bias. Any significant changes to the analyses described in this protocol will be highlighted in the SAP and the Clinical Study Report.

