## **9.3 Procedures for Eliciting, Recording, and Reporting Adverse Events**

### **9.3.1 Adverse Event Reporting Period**

The study period during which all AEs and SAEs must be reported begins after informed consent is obtained and ends 28 days after the ET/EOT Visit Date (ie, completion of 4-week ET Follow-up visit for the Early Terminated subjects and completion of End of Study (EOS) visit for the Completed subjects) except for pregnancy reporting ([Section 9.3.6](#)). In addition, all AEs reported spontaneously by the subject to site personnel, outside the study period, may be recorded.

Adverse events will be followed until resolved, stable, or until the subject’s last study visit or lost to follow-up. If an AE is not resolved or stabilized at the subject’s last visit, it is up to the discretion of the Investigator and study Medical Monitor to determine if further monitoring of the event is warranted.

Adverse events collected prior to dosing of study drug will be considered “nontreatment emergent” while those reported after the first dose of study drug and up to 28 days after the last dose of study drug will be considered “treatment emergent” and be assessed for relationship to study drug.

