10 PRIOR AND CONCOMITANT MEDICATIONS

The World Health Organization Drug Dictionary (WHO Drug) will be used to classify prior and concomitant medications by therapeutic class and generic name based on ATC code level 3. Prior medication is defined as any medication taken and stopped prior to the first dose of the study medication. Concomitant medication is defined as any medication taken between the day of first dose of the study medication and the day of last study medication date + 28 days.

Medication start and end dates and times will be compared with the start date of study drug and classified as per Table 3.

In case of partial or missing dates, comparisons will be made based on the level of detail available. For example, if start date of study drug is 04Jan2013, and a medication has a start date of Jan2013 but missing day, the medication will be classified as concomitant.

Table 3: Classification of prior and concomitant medications

Start date \ End date	Before start of study drug administration	On or after start of study drug administration	Missing
Before start of study drug administration	Prior	Concomitant	Concomitant
On or after start of study drug administration	–	Treatment Emergent Concomitant	Treatment Emergent Concomitant
Missing	Prior	Concomitant	Concomitant

Both prior and concomitant medication usage will be summarized by the number and proportion of subjects in each treatment group. Subjects will only be counted one time in each unique ATC Class and generic name if multiple drugs are used by a subject.

Detailed analyses may be performed on prior and concomitant medications of special interests such as oral iron, blood pressure medications and lipids medications.

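### SAP 12.1.1 ends TEAE counting at 7 days or at an undefined other anemia drug, against the protocol's 28 days, and its wording can be read to drop on-treatment events after an ESA

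*SAP*

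**What the plan says.** SAP 12.1.1 states its rule twice. The first sentence counts new or worsened events up to 7 days after the last dose or "until the administration of another anemia drug (other than the randomized treatment"). The second gives the exclusion: "An AE that occurs more than 7 days after the last dose of study medication or after the administration of another anemia drug" (again, other than the randomized treatment) is not a TEAE. The other drug is not defined there or elsewhere in the visible SAP. The section does not say whether counting restarts when study drug is resumed.

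The protocol has a longer window with two anchors. Section 8.4.4.1 says: "An AE that occurs more than 28 days after the EOT/ET visit date will not be counted as a TEAE". Section 9.3.1 runs from the last dose: "those reported after the first dose of study drug and up to 28 days after the last dose of study drug will be considered" treatment-emergent. Neither stops at another drug. Section 8.4.5 adds: "Any significant changes to the analyses described in this protocol will be highlighted in the SAP and the Clinical Study Report".

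Four related provisions matter:
- SAP 10 keeps a 28-day tail for concomitant medication, taken "between the day of first dose of the study medication and the day of last study medication date + 28 days".
- SAP 11 (Efficacy Emergent Period) and 11.3.2 (hospitalizations) use 7 days.
- SAP 11.3.7 uses the TEAE concept for an outcome: "Time to a treatment-emergent AE of vascular access thrombosis".
- Protocol 8.4.4.1 plans rates: "Treatment emergent adverse events of interest will also be reported in terms of incidence rate per PEY". SAP 9.1 ends PEY at the last dose.

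**The concern.** Safety against epoetin alfa is part of the primary objective, and the TEAE definition decides which events enter the main safety tables. Two things look wrong.

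First, the SAP shortens the protocol's window by 21 days and adds a stop that the protocol lacks. The visible text gives no reason and does not highlight the change.

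Second, the exclusion sentence joins its two limits by *or*, and nothing confines the drug limit to the time after study drug ends. Protocol 3.6.3.2 lets roxadustat subjects resume after a course of ESA rescue, or stay on study after an inadvertent or hospital ESA. Protocol 3.5.3.3 says that hospital ESA is not a deviation when roxadustat is not allowed or available. Taken literally, such a subject's later on-treatment events are not TEAEs. Epoetin alfa in a control subject is the randomized treatment and never triggers the cut. At stake are the TEAE and TESAE tables and the vascular access thrombosis analysis.

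**Working it through.** The plan states no figure on this point, so there is none to reproduce. The check sets the rules side by side and then sizes each reading.

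**1. The windows**

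| Source | Tail | Anchor | Stop at another drug |
|---|---|---|---|
| Protocol 8.4.4.1 | 28 days | EOT/ET visit | No |
| Protocol 9.3.1 | 28 days | Last dose | No |
| SAP 12.1.1 | 7 days | Last dose | Yes, undefined |

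The gap from the last dose is 28 − 7 = 21 days. As a share of the 28-day window (treatment days plus 28):
- 24 weeks: 21/(168 + 28) = 10.7%
- 52 weeks: 21/(364 + 28) = 5.4%

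The rule is the same in both arms, so these shares are equal if exposure is equal.

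**2. The drug trigger, by reading**
- *Tail reading:* the trigger only shortens the 7 days after the last dose. No on-treatment event is lost.
- *Literal, ESA only:* on-treatment events after an ESA are lost. This falls mainly on roxadustat, because ESA rescue exists only in that arm. A control subject given an ESA other than epoetin alfa is cut too.
- *Literal, iron included:* oral iron is encouraged for all subjects (protocol 3.6.2.1), so both arms are cut and the direction is undetermined.

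**3. Size on the literal, ESA-only reading**

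For one subject, with assumed timings: an ESA at Week 12 and treatment to Week 52 leaves 84 days counted. The loss is 364 − 84 = 280 of 364 on-treatment days, or 77%. An ESA at Week 26 loses 50%.

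For the roxadustat arm, the assumptions are: a share p is cut at mid-exposure of 52 weeks, the hazard is constant, and true incidence is I. The documents do not give p.
- Incidence recorded in a cut subject = 1 − (1 − I)^0.5: 5.13% for I = 10%, 29.29% for I = 50%.
- Understatement = p × (I − recorded incidence).

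The last two columns show the loss if events in a 4-week ESA course are set aside. The reference incidence is then 1 − (1 − I)^(48/52), which is 9.27% and 47.26%.

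| p | I = 10% | I = 50% | I = 10%, course set aside | I = 50%, course set aside |
|---|---|---|---|---|
| 5% | 0.24 | 1.04 | 0.21 | 0.90 |
| 10% | 0.49 | 2.07 | 0.41 | 1.80 |
| 20% | 0.97 | 4.14 | 0.83 | 3.59 |

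Entries are percentage points. The 4-week netting ignores the off-drug days before and after the ESA in protocol 3.6.3.2.

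**4. Rates per PEY**

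On the same reading, events stop at the ESA while PEY runs to the last dose. If a share f gets an ESA after a fraction t of exposure, the rate is multiplied by 1 − f(1 − t). That is 1 − 0.02 × 0.25 = 0.995 at the mild end of the assumed range and 1 − 0.20 × 0.75 = 0.85 at the other.

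The tail also puts event time outside PEY. A 28-day tail adds 28/168 = 16.7% (24 weeks) or 28/364 = 7.7% (52 weeks). A 7-day tail adds 7/168 = 4.2% or 7/364 = 1.9%.

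**The case against.** The strongest defence is that SAP 12.1.1 describes a tail rule. Its first sentence pairs the drug stop with the 7-day limit. Protocol 6.1.2.5 lets an ESA start 3 days after the last roxadustat dose, so a cut at the switch keeps events under a new treatment out of the study-drug tables. Seven days also matches SAP 11 and 11.3.2, and step 4 shows that it fits PEY better than 28 days. The 28-day concomitant-medication window serves another purpose and proves no error. The front pages of the SAP and the table shells were not available here, and protocol 8.4.5 also points to the Clinical Study Report.

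Much of this stands. The 7-day tail may be deliberate, and on the tail reading there is no comparative bias from the drug trigger. The consequence is also limited:
- Safety tables are descriptive (protocol 8.2).
- SAE, discontinuation and death listings remain, and death and fatal-SAE incidence is not expressly tied to TEAEs.
- Hospitalizations in SAP 11.3.2 have no drug trigger.
- Adjudicated events go to the pooled plans.

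The defence does not make the exclusion sentence say what it may have meant. It does not define the drug or reconcile the window with the protocol.

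A reader might infer that the SAP biases the safety comparison in favour of roxadustat. The documents do not support that. It needs the literal reading, an ESA-only definition and enough ESA use to matter. Control subjects given a different ESA are also cut, and no usage rate is given. Nor does the shorter tail alone favour an arm.

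**Conclusion.** The point holds as a conflict between protocol and SAP, together with an ambiguous and undefined stopping rule. Confidence in those two findings is high. The SAP should be amended, but the consequence is limited.

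The 21-day difference applies to both arms and is an inconsistency, not a shown bias. Any loss of on-treatment events is conditional on the literal reading. If ESAs alone count, it falls mainly on roxadustat, with the net size unknown. The 0.24 to 0.97 points at 10% incidence and 1.0 to 4.1 points at 50% illustrate that case, before any offsetting cuts in the control arm. They rest on an assumed share of 5% to 20%, mid-exposure timing, 52 weeks of treatment and a constant hazard.

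**What to change.** Amend SAP 12.1.1 and the sections that depend on it:

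1. Let another anemia drug end TEAE counting only after the last dose of study drug.
2. Define the term, for example by the ESA list in SAP 11.3.4.2 (B03XA01 to B03XA04), and say whether iron and transfusion count. That list puts epoetin alfa and other epoetins under one code, so also say how a non-randomized epoetin in a control subject is treated.
3. Count AEs during an ESA course in subjects who resume roxadustat as TEAEs, as protocol 8.4.4.1 and 9.3.1 imply. Identify them separately or remove them in a labelled sensitivity count.
4. Reconcile the two 28-day anchors, present the protocol's 28-day set beside the 7-day on-treatment set, and highlight the departure under protocol 8.4.5.
5. State that the same definition governs SAP 11.3.7, and how it combines with the Efficacy Emergent Period in SAP 11, which has no drug trigger.
6. For any TEAE rate per PEY, end exposure time on the date that event counting ends, in both arms and for either window.

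The cost is wording and one extra table set. AEs are already collected to 28 days after the ET/EOT visit (protocol 9.3.1). The downside is that the 28-day set will include some events after a switch: if an ESA starts 3 days after the last roxadustat dose, up to 28 − 3 = 25 tail days are ESA time.
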